5.5 Women of Childbearing Potential

Women of childbearing potential (WOCBP) includes any female who has experienced menarche and who has not undergone successful surgical sterilization (hysterectomy, bilateral tubal ligation, or bilateral oophorectomy) or is not postmenopausal. Menopause is defined as:

- Amenorrhea greater than or equal to 12 consecutive months without another cause and a documented serum follicle stimulating hormone (FSH) level $>$ 35mIU/mL

Or

- Woman with irregular menstrual periods and a documented serum FSH level $>$ 35mIU/mL

Or

NOTE: FSH level testing is not required for women greater than or equal to 62 years old with amenorrhea of greater than or equal to one year

- Woman on hormone replacement therapy (HRT)

For the purpose of this study, subjects who are WOCBP, MUST have a negative pregnancy test prior to randomization and administration of study medication. If during the course of the trial the subject is discharged for the remainder of the study, the subject should be abstinent and/or

use an acceptable method of birth control if they become sexually active. Acceptable methods of birth control are listed below.

- WOCBP and all men must use acceptable methods of contraception to avoid pregnancy throughout the study and for 90 days after the last dose of investigational product in such a manner that risk of pregnancy is minimized. The requisite drug interaction studies to determine the interaction of zavegeptant with oral contraceptives have not been performed to date. It is, therefore, not possible to determine the efficacy of oral contraceptives as an effective method of contraception for WOCBP or men with partners who are WOCBP who are participating this study. Oral estrogen and progestin hormonal contraceptives as a sole method of contraception are therefore prohibited.
- It is required that all WOCBP use two methods of contraception to prevent pregnancy, for the duration of the study (i.e. this study begins with signed consent form through 90 days after last dose of study drug). The two methods should include one barrier method (ex. condom with spermicidal gel, intrauterine devices, cervical cap etc.) and one other method. The other method could include hormonal contraceptives (e.g. oral contraceptives, injectable contraceptives, patch, or contraceptive implant) used since at least 4 weeks prior to sexual intercourse or another barrier method.
- Subjects who report abstinence, or who report exclusively being in same-sex relationships are still required to comply with the contraception requirements in this study to prevent pregnancy. These subjects must still be counseled on the requirement to avoid pregnancy throughout the study and for 90 days after the last dose of study medication, as well as acceptable methods of contraception to use during the study.
- All WOCBP must complete the pregnancy test schedule ([Table 1](#)).
- Male subjects must be willing not to donate sperm until 90 days following the last study drug administration.

5.6 Other Restrictions and Precautions

Not Applicable.

5.7 Deviation from Inclusion/Exclusion Criteria

Any significant event that does not comply with the inclusion/exclusion criteria, study conduct, or study procedures will be documented as a deviation. Deviations will be documented and reported through the clinical monitoring of the trial. Deviations will be reported to the IRB/EC at the frequency required by your IRB/EC. Prospective approval of protocol deviations to recruitment and enrollment criteria, also known as protocol waivers or exemptions, is not permitted.

6 STUDY CONDUCT AND DESCRIPTION OF STUDY PROCEDURES

6.1 Study Materials

The following study materials will be provided to the site:

- Investigator File/Study Binder
- Drug Accountability Logs (blinded and unblinded)
- IB
- eCRF Completion Instructions
 - eCRFs will be prepared for all data collection fields
- Drug Administration Instructions
- Laboratory manual, laboratory kits for PK and labels for CGRP samples will be provided. PK samples and CGRP samples will be shipped to a central laboratory for analysis
- Local laboratory collection will be used for this study and performed via hospital procedures for all labs with the exception of any experimental biomarkers that local labs are not able to perform (see Section [6.3.5.2](#))
- Experimental Predictive Biomarkers Collection and Processing Instructions. For experimental biomarkers that cannot be done at the local lab, instructions have been provided to order tests through a central laboratory for analysis and reporting.
- SAE Forms and SAE instructions
- Pregnancy surveillance forms and reporting instructions
- Instructions for NEWS2 and SOFA assessments for data entry

6.2 Eligibility Assessments

Informed consent, inclusion/exclusion criteria including medical history, concomitant medications and procedures, and laboratory assessments should be completed as outlined in [Table 1](#). Any eligibility assessments completed within 48 hours of signing Informed Consent may be used as the Screening assessments. The start of non-invasive supplemental oxygen should be captured on the concomitant procedures page.

6.3 Safety Assessments

6.3.1 Vital Signs and Physical Measurements (Height and Weight)

Body weight and height will be recorded at the scheduled visits as outlined in [Table 1](#). While in the hospital, vital signs and SpO₂, and FiO₂ will be collected daily and entered into the eCRF. The site staff should collect this around the same time every day within 3 hours, and the collection for the purpose of data entry into the eCRF should correlate to the time the NEWS2 is collected (AM or PM). Vital signs, SpO₂ and FiO₂, and NEWS2 assessments should be done at any in-patient or in-person visit up to Day 60. Although not a required protocol assessment, If ABG is collected from Screening through Day 29 as per SOC, this data should be entered in the eCRF in Unscheduled Visit ABG pages whenever it is collected.

6.3.2 Electrocardiogram (ECG)

A standard 12-lead ECG will be collected per protocol at the Screening Visit. If an ECG is collected as per SOC within 48 hours of signing Informed Consent, this may be used as the Screening ECG. If ECGs are collected as per SOC on Days 1 through 29, these values should be entered into the eCRF in Unscheduled Visit ECG pages if they are determined to be clinically significant. The Investigator will determine if any abnormalities are of clinical significance.

6.3.3 Chest x-ray

A standard chest x-ray will be recorded at the screening visit and at the EOT or Day 15 visit as per [Table 1](#). A chest x-ray collected within 48 hours of signing Informed Consent may be used as the Screening chest x-ray. If a chest-x-ray is collected as per SOC after Day 15 out to Day 29, the data should be collected in the eCRF in Unscheduled Visit Chest x-ray pages. The Investigator will determine if any abnormalities are of clinical significance.

6.3.4 Physical Exam

Subjects will undergo a physical examination (PE) at the scheduled visits as outlined in ([Table 1](#)). If a full PE is performed within 48 hours of signing Informed Consent, it may be used as the Screening PE. The directed physical exam should be guided by the subject's signs and symptoms.

6.3.5 Laboratory Assessments

The investigator must review all laboratory reports, document this review, and record any clinically significant relevant changes occurring during the study in the AE section of the eCRF (see guidance in [Section 8.4.2](#)). The laboratory reports must be filed with the source documents. Clinically significant abnormal laboratory test findings are those which are not associated with the underlying disease, unless judged by the investigator to be more severe than expected for the subject's condition.

All laboratory tests with abnormal values collected through Day 29 considered to be clinically significant by the Investigator should be reported as adverse events and repeated and recorded in the eCRF until the values return to normal or baseline or are no longer considered clinically significant by the investigator or medical monitor. Abnormal laboratory test values related to an SAE should continue to be recorded out to Day 60.

If such values do not return to normal/baseline within a reasonable period of time judged by the investigator, the etiology should be identified, and the sponsor notified.

All protocol-required laboratory assessments must be conducted in accordance with [Table 1](#).

If laboratory values from non-protocol specified laboratory assessments performed as per SOC require a change in subject management or are considered clinically significant by the investigator (e.g., SAE or AE), then the results must be recorded in the eCRF.

6.3.5.1 *Safety Laboratory Testing*

Blood and urine samples will be obtained as outlined in [Table 1](#) for clinical laboratory evaluations. If clinical labs are collected within 48 hours of signing Informed Consent, they may be used as the Screening labs. Laboratory samples will be collected and processed via hospital/site standard operating procedure (SOP).

Clinical Safety Labs:

- **Hematology:** red blood cell (RBC) count, hemoglobin, hematocrit, platelets, white blood cell (WBC) count, and differentials (neutrophils, basophils, eosinophils, lymphocytes, monocytes, bands)
- **HbA1c**
- **Chemistry:** albumin, calcium, creatinine kinase (CK), serum glucose, LDH, total protein, potassium, sodium, uric acid, blood urea nitrogen (BUN), serum creatinine, chloride, and bicarbonate
- **eGFR and method of calculation**

LFTs:

- AST, ALT, alkaline phosphatase, total bilirubin, direct bilirubin, and indirect bilirubin

Urinalysis:

- pH, specific gravity, ketones, nitrites, urobilinogen, leukocyte esterase, urine protein, urine glucose, and blood

CCI

© 2019 Pearson Education, Inc.

This figure displays a 5x4 grid of 20 black and white images, showing the progressive reconstruction of a handwritten digit '4' from a noisy input. The images are arranged in five rows and four columns. The first row shows the original noisy input. The second row shows the first two iterations of the reconstruction process. The third row shows the third and fourth iterations. The fourth row shows the fifth and sixth iterations. The fifth row shows the seventh and eighth iterations. The images show the digit becoming increasingly clear and well-defined as the reconstruction process progresses.

CCI

6.3.5.4 *SARS-CoV-2 Antibody Testing*

The serum antibody test should be done no earlier than Day 15 and before Day 60. The test should be performed by the hospital local lab or can be sent to a Central Lab if an account has been set-up by the Sponsor for the site.

6.3.5.5 *Pregnancy Testing*

Pregnancy tests will be conducted (serum or urine), when appropriate and as outlined in [Table 1](#).

6.4 Efficacy Assessments

6.4.1 *6-point ordinal scale*

A 6-point ordinal scale will be collected for the Primary and secondary endpoints. The scale consists of the following anchor points:

1. Death
2. Hospitalized, on invasive mechanical ventilation or ECMO
3. Hospitalized, on non-invasive ventilation or high flow oxygen devices
4. Hospitalized, requiring supplemental oxygen
5. Hospitalized, not requiring supplemental oxygen
6. Not hospitalized

The 6-point ordinal scale will be collected each day the subject is in the hospital and at all in-person or telephone visits.

6.5 Other Assessments

6.5.1 National Early Warning Score (NEWS2)

The NEWS2 is a validated tool for assessing physiological risk in deteriorating subjects and is based on a simple aggregate scoring system in which a score is allocated to physiological measurements, already recorded in routine practice, when subjects present to, or are being monitored in the hospital.⁴⁵ Six simple physiological parameters form the basis of the scoring system: 1) respiration rate; 2) oxygen saturation; 3) systolic blood pressure; 4) pulse rate; 5) level of consciousness or new confusion; and, 6) temperature.

6.5.2 Sequential Organ Failure Assessment (SOFA) Score

The (SOFA score, previously known as the sepsis-related organ failure assessment score, is used to track a person's status during the stay in an ICU to determine the extent of a person's organ function or rate of failure^{8,46-51}. The score is based on six different scores, one each for the respiratory, cardiovascular, hepatic, coagulation, renal and neurological systems. The higher the SOFA score, the higher the likely mortality.

6.5.3 COVID-19 Characteristics and Outcomes

Biohaven will collect several data points to better understand the current COVID-19 characteristics and outcomes with regard to how hospitals are managing in the current environment secondary to this disease. The datapoints will include (but not limited to) the following:

- When collecting SAEs with an outcome of death, collect whether the death occurred after withdrawal of care, and if so the reason for withdrawal of care
- Supportive measures received by subjects who progress to ARDS within the study (e.g., proning, paralytics etc.)
- Data collection on clinical decision-making that guides removal of a subject from mechanical ventilation in relation to their clinical deterioration or lack of clinical response (e.g., change in status to comfort measures, poor prognosis for recovery, allocation of resources in a pandemic setting etc.)
- Collection upon study entry of reason for hospital admission, standard of care followed for each subject at a site and if care decisions are made based on resource limitation
- Collection of any new infection that occurs during the study, (i.e., viral or non-viral), including the site of infection and source of culture (BAL, Tracheal aspirate, sputum, blood, urine etc.)
- Collect the number of days between onset of symptoms and initiation of treatment with zavegeptant

6.6 Early Discontinuation from Investigational Product

Subjects must discontinue investigational product for any of the following reasons:

- Withdrawal of informed consent (subject's decision to withdraw for any reason)
- Subject's eGFR decreases to < 15 mL/min
- Subjects who are discharged from the hospital prior to completing the treatment period

All subjects who discontinue treatment should still comply with remaining study visits and procedures as outlined in [Table 1](#).

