4.3 Schedule of Assessments

Table 1: Schedule of Assessments

Procedure	Screening Visit Day -2 to Day 1	Baseline Visit (Randomization) Day 1	Days 2 through 14 (+/- 1 day)¹	End of Treatment (EOT) Visit or Day 15 (+/- 1 day)²	Post-Treatment Phase Days 16 (+/- 1 day) through Day 29³ (+/- 2 days)	Day 60 (+/- 15 days)	Comments
Informed Consent	X						
Inclusion / Exclusion Eligibility Criteria	X	X					COVID-19 test should be positive by PCR test prior to study entry.

¹ If subjects are planned for release from the hospital prior to Day 15, they should discontinue drug for at least 24 hours and receive the End of Treatment assessments prior to discharge. They will be discontinued from study drug but continue in the study. All early discontinuations should be discussed with the Medical Monitor prior to planned release. Subjects will have follow-up phone calls on Days 15, 22, and 29 to assess 6-point ordinal scale, AEs/SAEs, and concomitant medications & procedures unless they are able to return for in-person visits. Subjects will need to return for at least 1 in-person visit on or before Day 60 to have the complete set of Day 29 assessments completed.

² EOT assessments should be completed after the last dose of study drug is administered and prior to hospital discharge. If the subject remains in the hospital and completes treatment (42 doses), Day 15 assessments are the same as EOT assessments. If the subject has EOT assessments completed prior to Day 15, then the Day 15 visit is a telephone visit.

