Concomitant Medication Collection	X	X	X	X	X		Concomitant medications are captured from first dose of study drug through Day 29.
Concomitant Procedures Collection	X	X	X	X	X		Concomitant procedures are captured from first dose of study drug through Day 29 except for the start of supplemental oxygen which could start within 48 hours of randomization. This data should be captured on the concomitant procedures page.
AE Assessment		X	X	X	X		Non-serious AEs are captured from first dose of study drug through Day 29. Non-serious adverse events should be followed until conclusion or stabilization or reported as SAEs if they become serious. Follow-up is also required for non-serious AEs that

Procedure	Screening Visit Day -2 to Day 1	Baseline Visit (Randomization) Day 1	Days 2 through 14 (+/- 1 day)¹	End of Treatment (EOT) Visit or Day 15 (+/- 1 day)²	Post-Treatment Phase Days 16 (+/- 1 day) through Day 29³ (+/- 2 days)	Day 60 (+/- 15 days)	Comments
							cause interruption or discontinuation of study drug or those that are present at Day 29. Note: For this study, admission and discharge to the ICU should be captured on the Adverse Event eCRF.
SAE assessment	X	X	X	X	X	X	
SAEs are captured any time after signing consent through the Day 60 visit.
 
All SAEs should be followed until resolution or stabilization.

Administer study drug		X	X				
IP is dispensed every 8 hours (+/- 2 hours) during the Treatment Phase for a total of 42 doses.
 
If subjects are discharged from the hospital to home prior to Day 15 they will be discontinued from study drug but continue in the study. Please note that due to the potential for rebound from withdrawal of an immunomodulating agent, subjects who are planning to be discharged should be off of study drug for at least

Procedure	Screening Visit Day -2 to Day 1	Baseline Visit (Randomization) Day 1	Days 2 through 14 (+/- 1 day) ¹	End of Treatment (EOT) Visit or Day 15 (+/- 1 day) ²	Post-Treatment Phase Days 16 (+/- 1 day) through Day 29 ³ (+/- 2 days)	Day 60 (+/- 15 days)	Comments
							24 hours before release from the hospital. If the subject is discharged to a step-down or satellite care facility where they can be monitored for safety, they should continue receiving study drug until completing 42 doses.

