4.3.3.2 *If Subjects are Discharged Prior to Day 15*

If a subject is planned to be discharged from the hospital prior to completing treatment, they will be discontinued from study drug. The Investigator should discuss the discharge plan with the Medical Monitor.

Note: Due to the potential for rebound from withdrawal of an immunomodulating agent, if a subject is withdrawn from drug, they need to be monitored in the hospital for at least 24 hours before release. All End of Treatment (EOT) assessments (see Section 4.3.5) should be collected after the patient's last dose of study drug and prior to discharge. Although subjects will be discontinued from the study drug, they will remain in the study. If possible, subjects should continue with in-person visits as per [Table 1](#). If this is not possible due to COVID-19 restrictions, a phone call should be made to the subject on Days 15, 22, and 29 to collect these assessments: 6-point ordinal scale, AEs/SAEs, and concomitant medications and procedures. If

the subject is unable to return for in-person visits on Days 22 and 29 due to quarantine, subjects will need to return for at least 1 in-person visit on or before Day 60 to have the Day 29 in-person assessments completed.

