7.2 Dose and Administration

Subjects who are hospitalized will be administered three doses (IN devices) per day of blinded IP (10 mg or matching placebo) to be dosed approximately 8 hours (+/- 2 hours) apart, for up to 14 days (42 doses) of treatment. When possible, if subjects are discharged from the hospital to another acute care medical facility prior to completing treatment, they will be provided with enough of their blinded IP and dosing instructions to continue their Q8h regimen until 42 doses have been completed.

Subjects who are discharged to home prior to completing treatment will be discontinued from study drug. Procedures indicated in Section 4.3.3.2 should be followed.

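### Section 6.6 and Table 1 footnote 1 stop study drug on any discharge from the hospital, while the Table 1 dosing row continues it to 42 doses after discharge to a step-down or satellite facility

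*Protocol*

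**What the plan says.** Three places stop study drug without naming a destination.

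- Section 6.6 opens with "Subjects must discontinue investigational product for any of the following reasons" and includes in its list "Subjects who are discharged from the hospital prior to completing the treatment period".
- Table 1, footnote 1: "If subjects are planned for release from the hospital prior to Day 15, they should discontinue drug for at least 24 hours". It adds that these subjects come off study drug but stay in the study.
- Section 4.3.3.2: "If a subject is planned to be discharged from the hospital prior to completing treatment, they will be discontinued from study drug".

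Four places make the outcome depend on destination, or assume that dosing goes on after a move.

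- The Table 1 row on administering study drug separates two cases. For home: "If subjects are discharged from the hospital to home prior to Day 15 they will be discontinued from study drug". For a subject who "is discharged to a step-down or satellite care facility where they can be monitored for safety, they should continue receiving study drug", the course runs to 42 doses.
- Section 4.3.3.1 keeps subjects on drug when they are transferred to another care facility.
- Section 7.2 supplies drug to dose 42, when possible, "if subjects are discharged from the hospital to another acute care medical facility prior to completing treatment". It stops drug on discharge to home and sends those subjects to Section 4.3.3.2.
- Section 7.4 says that compliance and accountability checks continue for subjects discharged to another care facility.

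**The concern.** Section 6.6 is where a site looks for its stopping rules, and its wording is mandatory. The Table 1 dosing row is where a site looks for what to do at the next dose. For a subject leaving the hospital for a non-acute step-down or satellite facility, the two give opposite instructions.

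Three things follow from the choice:

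- how much drug the subject receives before the Day 15 primary rating;
- whether the subject is held in hospital off drug for at least 24 hours, a precaution the protocol ties to possible rebound after withdrawal;
- when the EOT assessments take place, and whether Day 15 becomes a telephone visit.

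Two subjects in the same situation could be handled differently, and one would be recorded as an early discontinuation while the other would not.

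**Working it through.** The conflict is one of text, so the first step is to set the sections side by side and read each literally.

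| Section | Home | Another acute care facility | Non-acute step-down or satellite facility |
|---|---|---|---|
| 6.6 | stop | stop | stop |
| Table 1 footnote 1 | stop | stop | stop |
| 4.3.3.2 | stop | stop as worded; home only if read through 7.2 | stop as worded; home only if read through 7.2 |
| Table 1 dosing row | stop | not named as such | continue to 42 doses |
| 4.3.3.1 | not addressed | continue on transfer | continue on transfer |
| 7.2 | stop | continue when possible | silent |
| 7.4 | not addressed | dosing assumed to continue | dosing assumed to continue |

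Only the home column is consistent. In the last column, 6.6 and footnote 1 stop drug while the dosing row, 4.3.3.1 and 7.4 continue it.

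Could the word discharged in 6.6 mean discharged home, with moves between facilities called transfers? The protocol's own usage does not allow that. The Table 1 dosing row, 7.2 and 7.4 all use discharged for moves after which dosing continues. The dosing row and 7.2 add the word home when they mean home; 6.6 does not.

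The facility labels also vary: step-down or satellite care facility (dosing row), another care facility (4.3.3.1 and 7.4), another acute care medical facility (7.2) and recovery facility (Table 1 footnote 3). Nothing says how they map onto each other.

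Doses at stake. Inputs: one dose every 8 hours for 14 days (Section 4.1).

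- Full course: 24 / 8 = 3 doses a day; 3 × 14 = 42, which reproduces the protocol's figure.
- Dosing stops at the end of Visit Day 5: 3 × 5 = 15 given; 42 − 15 = 27 remain; 27 / 42 = 64%.
- Dosing stops at the end of Visit Day 10: 3 × 10 = 30 given; 42 − 30 = 12 remain; 12 / 42 = 29%.

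These figures assume no missed doses and count from the last dose under the stopping text. If the day is instead that of the physical move, the 24-hour hold removes at least 3 more doses: 30 of 42 (71%) for Day 5 and 15 of 42 (36%) for Day 10. The days are illustrations, not estimates of when such moves occur.

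Visit consequences. Under Section 4.3.5, an EOT visit before Day 15 makes Day 15 a telephone visit. A subject who stops on leaving has an early EOT; one who continues has EOT after dose 42, at about Day 15.

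**The case against.** The strongest answer is that most of the protocol already sorts subjects by destination. The dosing row, 4.3.3.1 and 7.4 agree that drug continues at a facility, and 7.2 agrees for acute ones. Section 7.2 ties 4.3.3.2 to discharge home, and the telephone calls, quarantine and return visits in 4.3.3.2 fit that reading. This much stands: 4.3.3.2 should not be counted as a second, independent contradiction. A reader might also infer that 7.2 contradicts Table 1. It does not; it is silent on non-acute facilities.

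Second, the Medical Monitor is involved. Footnote 1 and 4.3.3.2 call for discharge plans and early discontinuations to be discussed with that role, and 4.3.3.1 refers questions about transferred subjects there. That makes divergence between sites less likely. It does not supply a written rule to apply.

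Third, the effect on the primary result is limited. Subjects taken off drug stay in the study, the 6-point scale is collected at telephone as well as in-person visits, and the efficacy set requires only one dose. The ambiguity is the same in both blinded arms. All of this stands.

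What the objection does not remove is a mandatory stopping item in 6.6, and a matching footnote, that contradict the dosing row on their face.

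**Conclusion.** The protocol contradicts itself on whether a subject discharged to a non-acute step-down or satellite facility stops or continues study drug. The conflict lies between 6.6 and Table 1 footnote 1 on one side and the Table 1 dosing row, 4.3.3.1 and 7.4 on the other; 4.3.3.2 shares the general wording but has a reasonable home-only reading. For such a subject, 27 of 42 doses are in question if dosing would stop at the end of Visit Day 5 and 12 of 42 at the end of Visit Day 10, assuming none were missed. The hold, EOT timing and Day 15 visit mode go with it.

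Three stronger conclusions are tempting, and the protocol does not support them:

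- That a sizeable share of subjects is affected because only about 2 to 5 sites are planned. The number of sites says nothing about how many subjects go to such facilities before dose 42, and the protocol gives no figure.
- That the primary comparison is biased or Day 15 ratings are lost. Ratings continue off drug and by telephone, and no analysis set, alpha, power or sample-size figure changes. The plausible effect is inconsistent exposure and handling.
- That the case report form lacks a field for discharge destination. The form is not shown, so this cannot be judged.

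**What to change.** Reconcile Section 6.6, Table 1 footnote 1 and Section 4.3.3.2 with the Table 1 dosing row and Sections 4.3.3.1, 7.2 and 7.4. State the sponsor's chosen rule once, most naturally in 6.6, for each named destination: home, another acute care hospital, and a non-acute step-down, satellite or recovery facility. Use one set of facility terms throughout. For each destination, say whether the 24-hour hold applies, when EOT assessments are done and how the Day 15 visit is conducted. The other sections should refer to that statement and not restate it. Which rule applies to which destination is for the sponsor to decide.

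The cost is wording in seven places of one amendment, with a matching note to sites. No analysis, sample size or endpoint definition has to change.
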